### 10.1 Dosing and Administration

#### Interferon-Enhancing Regimen

For dosing, refer to **Table 1**. The regimen will be administered on Days 1 and 3 (or 4) in the following order:

- Pretreatment: 500 mL Normal saline IV over 60 minutes
- Pre-medications: acetaminophen (Tylenol®) 650 mg by mouth x 1 dose; prochlorperazine (Compazine®) 10 mg by mouth x 1 dose – administered 30 minutes ( $\pm$ 5 minutes) after starting pre-treatment hydration
- Interferon alpha-2b: (dose-escalation; maximum 20 MU/M $^2$ ) IV over 20 minutes

Rintatolimod: 200 mg IV, initial administration to start at 20 mL/ hour and increase to 40 mL/ hour after 30 minutes as per the standard at Roswell. Total duration of rintatolimod infusion: 2.5 h-3h. Tubing should be flushed with 30 to 50 mL of normal saline solution upon completion. Administration will be followed by 1 hour of observation and vital signs at 30 and 60 minutes post-infusion ( $\pm$  5 minutes).

Roswell Park Protocol No.: I-659920

Pretreatment and pre-meds listed above are recommendations and may be modified based upon institutional SOC requirements and at the discretion of the investigator. Treatment can be administered in the outpatient or inpatient setting, per the investigator's/physician's discretion.

Each daily treatment will be initiated after interval history and physical examination is performed and once the relevant laboratory studies have been confirmed to be within clinically acceptable ranges, specifically: ANC  $\geq$  1000/mm^3, total bilirubin  $\leq$  3x ULN, AST and ALT  $\leq$  5 x ULN.

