### **3.3 Inclusion Criteria (Expansion Cohort: Rintatolimod Plus Best Available Standard Care)**

We have added an expansion cohort to receive rintatolimod plus best available standard care. Because rIFN- $\alpha$  is not included in this group, eligibility criteria have been liberalized to include patients with more severe COVID-19, including those with respiratory failure, and exclusion criteria specific to rIFN- $\alpha$  have been removed. For patients who are eligible for both the main cohort and expansion cohort, enrollment in the Main Cohort will be prioritized because of the rationale that it might be more effective. To be included in the Expansion Cohort, cancer participants must meet the following criteria:

- 1 Patients with cancer or allogeneic stem cell transplant recipients with and without a cancer diagnosis.
  - Patients with cancer may be on active therapy or received therapy (e.g., chemotherapy, radiation, or surgery) within 7 years.
  - Patients with active cancer who have not yet been treated (e.g. newly diagnosed cancer or early stage MDS or CLL) are eligible.
  - Basal cell cancer and carcinoma in situ treated with local excision alone do not qualify for inclusion.
- 2 Presence of symptomatic infection, defined by fever ( $T \geq 38.0^{\circ}\text{C}$ ) OR respiratory symptoms (cough, nasal congestion, or shortness of breath) OR lung infiltrates by chest X-ray or CT imaging. Diagnosis of COVID-19 is based on PCR testing of respiratory samples. Severe infection is excluded (see Exclusion Criteria).
- 3 Age equal to  $\geq 18$  years or older (children are excluded because COVID-19 typically has a milder course in children, and lack of safety data of this regimen in children). In the absence of COVID-19, a life expectancy of 6 months is expected.
- 4 Participant or health care proxy must understand the investigational nature of this study and sign an Independent Ethics Committee/Institutional Review Board approved written informed consent form prior to receiving any study related procedure. There may be specific instances when the patient can't provide informed consent, e.g. they require mechanical ventilation and are sedated, in which case a health care proxy will be able to provide informed consent. Patients with temporary cognitive impairment will be consented once their capacity has returned. Patients with chronic cognitive impairment, e.g. dementia, that precludes informed consent will not be enrolled.

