## 10 TREATMENT

All patients will receive best available standard of care. Depending on the severity of COVID-19 and need for hospitalization, standard of care can include, but is not limited to, monoclonal antibody formulations directed against the SARS-CoV-2 Spike protein, remdesivir, dexamethasone, and tocilizumab. Treatment in the Main Cohort will consist of lead-in single agent rintatolimod (first 3 patients on the dose-escalation component) followed by the combination of rintatolimod and dose-escalation of rIFN $\alpha$ . Intravenous (IV) rintatolimod is administered as a fixed dose (200 mg per infusion) and IV rIFN $\alpha$  dose-escalation will be a standard 3 + 3 design, with the following doses per infusion: 0, 5, 10, and 20 MU/M $^2$ . The dose-escalation phase will lead to which patients will receive IFN $\alpha$  at 20 MU/M $^2$  or at MTD + rintatolimod (200 mg). The regimen will be administered on Day 1 and on Day 3 (or 4), and EOT assessments will occur on Day 7 ( $\pm$  1 day) and Day 14 ( $\pm$  3 days). This portion of the study will allow for additional safety data and the analysis of the effect of the study regimen on nasopharyngeal viral load. Using each patient's baseline nasopharyngeal viral load, we will evaluate to what extent the study regimen reduces viral load relative to supportive care only.

Treatment in the Expansion Cohort will be IV rintatolimod is administered as a fixed dose (200 mg per infusion on Day 1 and on Day 3 (or 4). Based on the PI's judgment, additional infusions of rintatolimod at 200 mg may be administered 3 to 4 days apart. Decisions about additional rintatolimod infusions will be based on evaluation of AEs attributed to rintatolimod, particularly increased FIO $_2$  needs. A maximum of 12 rintatolimod infusions may be administered per patient. The rationale for a maximum of 12 infusions was based on discussions with leadership from AIM Immunotech regarding the expected effects of rintatolimod on innate immune responses over time based on data from patients with and without cancer. Rintatolimod activates innate immune responses through a number of mechanisms including activation of RNase L and inducing interferon stimulated genes (ISGs). Administration of rintatolimod over a number of weeks may be required for sustained activation of innate immune responses to clear SARS-CoV-2.

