#### **Expansion Cohort (Rintatolimod plus best available standard of care)**

20 patients on Expansion Cohort will receive rintatolimod plus best available care.

Pretreatment for rintatolimod will be:

- 500 mL Normal saline IV over 60 minutes
- Pre-medications: acetaminophen (Tylenol®) 650 mg by mouth x 1 dose; prochlorperazine (Compazine®) 10 mg by mouth x 1 dose – administered 30 minutes ( $\pm$ 5 minutes) after starting pre-treatment hydration

Rintatolimod: 200 mg IV, initial administration to start at 20 mL/ hour and increase to 40 mL/ hour after 30 minutes as per the standard at Roswell. Total duration of rintatolimod infusion: 2.5 h-3h. Tubing should be flushed with 30 to 50 mL of normal saline solution upon completion. Administration will be followed by 1 hour of observation and vital signs at 30 and 60 minutes post-infusion ( $\pm$  5 minutes).

Pretreatment and pre-meds listed above are recommendations and may be modified based upon institutional SOC requirements and at the discretion of the investigator. Treatment can be administered in the outpatient or inpatient setting, per the investigator's/physician's discretion.

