**Table 2 Treatment Related Toxicity Management**

Treatment-related AEs	Toxicity grade or conditions (CTCAE5.0)	Action taken for Interferon Alpha-2b	Action taken for Rintatolimod	Additional actions
Chills/Fever	Grade 3 that persists for $\geq$ 48 hours despite acetaminophen	None	None	Consider additional acetaminophen dosing, supportive care
Pancreatitis	Grade 3	Hold  Decreased future doses by 75% (to 5MU/M2)	Hold	Supportive measures as clinically indicated
AST / ALT elevation or Increased bilirubin	Grade 3	Hold until improved to grade 1; Decrease future doses by 75%	Hold	Advise evaluation for other possible etiologies; consider imaging
Vomiting	Grade 3 vomiting $\geq$ 48 hours despite optimal anti-emetic therapy	Hold until resolved to grade 1; Decrease future doses by 75%	Hold	
Depression or other clinically relevant mood disorder	Grade 3	Permanently discontinue; appropriate supportive care/intervention	None	Patients and family members will be informed in advance about the potential for depression and anxiety, including worsening of pre-existing mood disorders.
Neutropenia	Grade 3 or 4	If Grade 3, decrease future doses by 75%. If Grade 4, permanently discontinue	Hold	Transient neutropenia is expected as a result of neutrophil activation and redistribution rather than bone marrow suppression. Recent cytotoxic chemotherapy is an additional cause of neutropenia. COVID-19 is known to cause lymphopenia, but not neutropenia. For prolonged neutropenia that is not expected from the study regimen and recent chemotherapy (if applicable), the primary oncologist and a hematologist will be consulted.
Hemorrhage	Grade 2 or greater	None	None	
Myocardial infarction, stroke,		Permanently discontinue; appropriate	Permanently discontinue; appropriate	

Treatment-related AEs	Toxicity grade or conditions (CTCAE5.0)	Action taken for Interferon Alpha-2b	Action taken for Rintatolimod	Additional actions
or other arterial thrombotic event		supportive care/intervention	supportive care/intervention	
All other clinically significant AEs 	Intolerable Grade 2 or Grade 3	Hold therapy until resolved to Grade 1 or baseline; reduce future doses by 75%	Hold therapy until resolved to Grade 1 or baseline; reduce future doses by 50%	
	Grade 4	Permanently Discontinue	Permanently Discontinue	

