### **10.4 Duration of Study Treatment**

A total of 2 daily doses over a 4-day day period of treatment is planned.

The participant may stop treatment earlier than planned in the event that the following occurs:

- Unacceptable toxicity
- Progression to severe COVID-19 infection, defined by new or worse pulmonary infiltrates on Chest X-Ray or CT imaging plus one of the following: room air  $\text{SaO}_2 \leq 92\%$ , room air  $\text{PO}_2 < 70 \text{ mm Hg}$ , or  $\text{PAO}_2-\text{PaO}_2 \geq 35 \text{ mm Hg}$ , and/or requiring mechanical ventilation
- Withdrawal of consent from study
- Participant non-compliance with study requirements

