### **11.1 Screening**

Within 3 days prior to treatment initiation and may be the same day as initiation of study treatment:

- Recording of concomitant medications
- Medical and Surgical History
- Physical exam (lung auscultation), Vital Signs and weight;  $\text{SaO}_2$
- ECOG Performance Status Assessment
- Hematology
- Chemistry
- Arterial blood gas

Roswell Park Protocol No.: I-659920

- Serum HCG pregnancy testing (within 3 days of Day 1 in women of child-bearing potential only)
- EKG
- Chest X-ray or CT imaging (NOTE: If a chest CT is ordered as standard of care prior to starting treatment, a chest x-ray is not required)
- Nasopharyngeal swab
- Evaluations Performed on each day of treatment [(Day 1 and Day 3 (+ 1 day)]: Recording of concomitant medications
- Recording of Adverse Events
- Targeted physical exam
  - Auscultation of lungs
  - Vital Signs (temperature, blood pressure, pulse rate and respiratory rate, SaO2) will be performed pre- treatment and at 30 and 60 minutes post rintatolimod ( $\pm$  5 minutes)
- ECOG Performance Status Assessment
- Hematology
- Chemistry
- Blood (30cc) for correlative studies: On Day 1 treatment and Day 3 treatment, prior to treatment and within 1 hour after end of infusion treatment (two draws on each of these days).
- Nasopharyngeal swabs for viral quantification by quantitative PCR

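### The Expansion Cohort may receive up to 12 rintatolimod infusions with no pre-dose laboratory check; in a full course at least 4 of the 10 extra infusions have no scheduled CBC/CMP in the previous 3 days

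*Combined protocol and SAP*

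**What the plan says.** **Pre-dose check.** Section 10.1, Interferon-Enhancing Regimen, requires an interval history and examination before each treatment. Dosing then proceeds "once the relevant laboratory studies have been confirmed to be within clinically acceptable ranges": ANC at least 1000/mm³, total bilirubin at most 3 × ULN, AST and ALT at most 5 × ULN.

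**Expansion dosing.** The next block of Section 10.1 opens "20 patients on Expansion Cohort will receive rintatolimod plus best available care". It repeats the hydration, pre-medication, infusion, observation and setting text, and has no laboratory condition.

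**Expansion eligibility.** Section 3.3 says "eligibility criteria have been liberalized to include patients with more severe COVID-19". Neither 3.3 nor 3.4 sets a laboratory limit. Section 3.1 sets platelet, haemoglobin, ANC, renal, hepatic and pancreatic limits for the Main Cohort.

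**Extra infusions.** Section 10 allows further 200 mg infusions 3 to 4 days apart on the investigator's judgment, up to 12 in total. "Decisions about additional rintatolimod infusions will be based on evaluation of AEs attributed to rintatolimod", with rising FiO2 need singled out. Long courses are foreseen: "Administration of rintatolimod over a number of weeks may be required for sustained activation of innate immune responses to clear SARS-CoV-2".

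**Laboratory schedule.** Section 11.1 lists hematology and chemistry under "Evaluations Performed on each day of treatment [(Day 1 and Day 3 (+ 1 day", so its bracket names only the two fixed days. Section 10.4 still reads "A total of 2 daily doses over a 4-day day period of treatment is planned". The Expansion calendar in Appendix F has CBC and CMP at screening, Day 1, Day 3 or 4, and one column for Day 7 (±1), Day 14 (±3) and Day 30 (±3). That column also carries the extra-infusion mark. Footnote 5, however, assigns the follow-up schedule to patients who receive no extra infusions.

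**Toxicity rules.** Table 2 holds rintatolimod for grade 3 "AST / ALT elevation or Increased bilirubin".

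**The concern.** The same drug at the same dose is checked in one cohort and not in the other. The Main Cohort's 0 MU/m² tier is rintatolimod alone, two infusions, in patients without severe COVID-19, and it falls under the regimen that carries the laboratory check. The Expansion Cohort may give up to twelve infusions, admits patients with respiratory failure, and has no such check.

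Three laboratory dates have to serve up to ten extra infusions, so the plan permits repeat dosing on an old liver result. Section 13.2 reports no dose-limiting liver toxicity in over 800 patients, at doses as high as 1200 mg twice weekly. It also reports liver enzyme rises in several patients with dosing over many weeks. The Table 2 hold, the grade 4 stopping rule, the AE-based decision on further infusions and DSMC review can act on a laboratory abnormality only if it has been measured.

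**Working it through.** The plan gives no figure to reproduce. The check counts extra infusions that lack a recent scheduled CBC/CMP.

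**Inputs**
- Infusion 1 on Day 1, infusion 2 on Day 3 or 4, then up to 10 more at gaps of 3 or 4 days (Section 10).
- CBC/CMP on Day 1, on the Day 3/4 visit, and once in each of the windows Day 6–8, 11–17 and 27–33 (Appendix F, Expansion calendar).
- Recency standard: a result on the infusion day or in the 3 days before. This is an assumption, taken from the screening window in Section 11.1; other standards are shown below.

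**Assumption in the plan's favour.** The Day 7/14/30 laboratory tests are taken to apply to patients on extra infusions, despite footnote 5, and no visit is missed.

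**Method.** Day of infusion *k* = day of infusion 2 + the sum of the (*k* − 2) gaps. This gives 2 × 2¹⁰ = 2,048 schedules and 3 × 7 × 7 = 147 visit-date sets. For each schedule, the visit dates that leave the fewest infusions uncovered were kept.

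**Length of a full course.** Earliest end: 3 + 10 × 3 = Day 33. Latest end: 4 + 10 × 4 = Day 44. Between 1 and 4 infusions fall after Day 30.

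**Two schedules by hand, 3-day standard**
- Second dose on Day 3, then every 3 days: extra infusions on Days 6, 9, 12, 15, 18, 21, 24, 27, 30, 33. With laboratory tests on Days 6, 12 and 27, the uncovered infusions are Days 18, 21, 24 and 33: 4 of 10.
- Second dose on Day 4, then every 4 days: extra infusions on Days 8, 12, 16, 20, 24, 28, 32, 36, 40, 44. With 4-day gaps, one test covers at most one infusion on this standard, so three visits cover at most three: 7 of 10 uncovered. Tests on Days 6, 11 and 27 achieve this.

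**Full 12-infusion course: uncovered extra infusions of 10 (range over schedules)**

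| Result no older than | Best visit dates | Nominal Days 7/14/30 |
|---|---|---|
| Same day | 7 | 7–10 |
| 3 days | 4–7 | 4–7 |
| 4 days | 3–4 | 4–7 |
| 7 days | 0–4 | 2–4 |

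The oldest result relied on before any infusion is 7 to 12 days old with the best visit dates and 12 to 15 days old on nominal dates.

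**Shorter courses, best visit dates**

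| Total infusions | Uncovered, 3-day | Uncovered, same-day |
|---|---|---|
| 4 | 0 | 0–1 |
| 5 | 0–1 | 1 |
| 6 | 0–2 | 2 |
| 7 | 1–3 | 3 |
| 9 | 2–4 | 4–5 |
| 12 | 4–7 | 7 |

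Every schedule has a gap from 7 total infusions on the 3-day standard, and from 5 on the same-day standard.

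**The case against.** **The bracket in Section 11.1 may simply be out of date.** That section, like 10.4, describes a two-dose regimen. Its treatment-day heading could be meant to cover extra infusion days, and the laboratory gap would then close. The text does not say so, and the dosing limits would still be missing from the Expansion block.

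**The count depends on chosen standards.** The 3-day window governs screening, Section 10.1 sets no maximum age for a result, and 12 infusions is a ceiling with no expected number given. This stands. On a 7-day standard, courses of up to 6 infusions have no gap even on nominal visit dates. The size must be read with its standard and course length.

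**The applicable schedule is itself unclear.** Footnote 5 makes it doubtful that the Day 7/14/30 tests apply to patients on extra infusions. Footnote 7 accepts missed outpatient assessments without calling them violations. Both points suggest the count may flatter the plan.

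**A result would be old, not absent.** On the printed calendar this is right: CMP is scheduled before any extra infusion. Inpatients may also have routine tests, but the protocol does not require them and treatment may be outpatient.

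**Other controls exist.** Table 2, the rintatolimod hold and reduction rule in Section 10.2.1, and the AE-based decision in Section 10 are real. For laboratory toxicity each needs a measured value, and none schedules a test.

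**The omission may be deliberate.** Interferon is absent, and the safety record in Section 13.2 is reassuring. But Section 3.3 removes only interferon-specific exclusion criteria and is silent on dosing checks, and the rintatolimod-alone tier of the Main Cohort keeps the check. The reassuring record argues for moderate urgency, not for leaving the gap.

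**Conclusion.** The concern holds. As written, the Expansion Cohort has no pre-dose laboratory condition, and its calendar does not follow the permitted dosing. In a full 12-infusion course, 4 to 7 of the 10 extra infusions have no scheduled CBC/CMP in the previous 3 days, even with the most favourable visit dates.

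This rests on the printed Day 7/14/30 tests applying to these patients, on Section 11.1 being read as its bracket is written, and on the borrowed 3-day standard. Patients with few infusions may be fully covered. The change should be made: it is a specific safety gap, at low cost, for a drug with reported liver enzyme rises on long dosing. No power or error-rate figure is affected.

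**What to change.** 1. Add a column to the Expansion calendar for each additional infusion, with CBC, CMP and AE review before dosing and a result no more than 3 days old.
2. Carry the bilirubin (≤ 3 × ULN) and AST/ALT (≤ 5 × ULN) limits into the Expansion block of Section 10.1, and state what applies to a patient who enters above them. Leave any ANC limit to the sponsor.
3. State that the Day 7/14/30 schedule also applies to patients who receive extra infusions. Align Sections 10.4 and 11.1 with the permitted number of doses.
4. Minor: record FiO2, or oxygen device and flow, with each SaO2. Rising FiO2 need is the one AE singled out for these decisions and is not a scheduled item, although it can be captured as an AE.

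**Cost.** About one paragraph and one calendar column. At most 10 routine draws per patient, or 20 × 10 = 200 in the cohort. Some doses may wait for a result, and the limits could delay dosing in a patient who entered with abnormal liver tests, which is why item 2 asks for a rule. The oxygen field needs no extra procedure.

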#### **Expansion Cohort (Rintatolimod plus best available standard of care)**

20 patients on Expansion Cohort will receive rintatolimod plus best available care.

Pretreatment for rintatolimod will be:

- 500 mL Normal saline IV over 60 minutes
- Pre-medications: acetaminophen (Tylenol®) 650 mg by mouth x 1 dose; prochlorperazine (Compazine®) 10 mg by mouth x 1 dose – administered 30 minutes ( $\pm$ 5 minutes) after starting pre-treatment hydration

Rintatolimod: 200 mg IV, initial administration to start at 20 mL/ hour and increase to 40 mL/ hour after 30 minutes as per the standard at Roswell. Total duration of rintatolimod infusion: 2.5 h-3h. Tubing should be flushed with 30 to 50 mL of normal saline solution upon completion. Administration will be followed by 1 hour of observation and vital signs at 30 and 60 minutes post-infusion ( $\pm$  5 minutes).

Pretreatment and pre-meds listed above are recommendations and may be modified based upon institutional SOC requirements and at the discretion of the investigator. Treatment can be administered in the outpatient or inpatient setting, per the investigator's/physician's discretion.

#### **10.2 Dose Modification**

Based on our experience with the combination of rintatolimod and INTRON® A as anti-cancer treatment (over longer periods of time than the currently proposed trial for COVID-19), we do not expect the need for dose modifications. However, in case of specific toxicities, dose modification rules will be used (**Table 2**). Taking into account that the rationale for the regimen is a short-term intervention to augment antiviral immunity for an acute viral infection, we do not plan for re-escalations or administration of any missing doses after successful management of toxicities. Since the progression of COVID-19 is believed to be facilitated by lack of the activation of innate immunity (IFN responses and RNases), we anticipate that even transient (or lower intensity) activation of these pathways may help to better control the viral spread. Toxicity will be assessed according to the NCI Common Terminology Criteria for Adverse Events Version 5.0 (CTCAE v5.0).

Therapy will be immediately discontinued for any grade IV treatment-related toxicity that becomes apparent. In the event of any adverse effect, appropriate medical treatment will be instituted and study treatment will be discontinued based on physician judgment.

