## **2.5 Rationale for eliminating celecoxib from the proposed regimen and for reducing, eliminating, or changing the source and route of administration of IFN $\alpha$**

In view of the potential concerns regarding the use of NSAIDs in patients with COVID-19, we decided not to include Celecoxib in the current trial.

The dose of INTRON® A IFN $\alpha$  may be reduced from 20MU/m^2 to 5 MU/m^2 or to 0), in case of any observed toxicities, or in case of IFN $\alpha$  shortage.

In case of potential shortages, INTRON® A may be replaced by another form of IFN $\alpha$  at the same (Units) dose. In case the only available IFN $\alpha$  is formulated for an alternative route of administration (e.g., subcutaneous), we will adjust the dose to use the most common dose for that specific product. An IRB amendment will be submitted for any changes in formulation or dosing.

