### 10.2.1 Interferon Alpha-2b and/or rintatolimod Non-hematologic toxicities

Considered to be possibly, probably, or definitely related to interferon alpha-2b and rintatolimod:

- **Interferon Alpha-2b:**

For grade 3 toxicity not addressed in Table 2:

- 1st episode: dose will be held and restarted at the next study visit at a dose reduction by 75%. The dose can be re-escalated if toxicity is reduced to ≤ grade 1 or baseline.
- 2nd episode: Treatment will be discontinued.

For grade 4 toxicity

- Treatment will be discontinued

Roswell Park Protocol No.: I-659920

- **Rintatolimod:**

For grade 3 toxicity not addressed in Table 2:

- 1st episode: dose will be held and restarted at the next study visit at a dose reduction by 50%. The dose can be re-escalated if toxicity is reduced to  $\leq$  grade 1 or baseline.
- 2nd episode: Treatment will be discontinued.

For grade 4 toxicity:

- Treatment will be discontinued

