### **32.2.2 Formulation and packaging**

Rintatolimod is supplied as a liquid solution in glass bottles containing 200 mg (100 mg in case of toxicity) per 80 mL. Rintatolimod is a colorless solution containing 2.5 mg/mL in physiological salts (0.15 M NaCl, 0.01 M phosphate, 0.001 M Mg++). The product does not contain preservatives or antioxidants.

Roswell Park Protocol No.: I-659920

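### Post-toxicity dosing text disagrees in two places: 5 MU/M2 in the Table 2 pancreatitis row is a 75% cut only from 20, and Section 10.2.1 restarts and re-escalates on terms that Table 2 and Section 10.2 do not share.

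*Combined protocol and SAP*

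**What the plan says.** **Pancreatitis row.** For grade 3 pancreatitis, Table 2 holds both drugs and adds for IFN: "Decreased future doses by 75% (to 5MU/M2". No other row attaches an absolute dose to its percentage. The IFN levels in Table 1 are 0, 5, 10 and 20 MU/M2. Section 2.5 says the IFN dose "may be reduced from 20MU/m 2 to 5 MU/m 2 or to 0), in case of any observed toxicities", so it describes the reduction from the top level only.

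**Re-escalation and restart.** Three texts bear on this.

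- Section 10.2, reasoning from a short-term intervention, says "we do not plan for re-escalations or administration of any missing doses after successful management of toxicities".
- The Table 2 row headed "All other clinically significant AEs" covers intolerable grade 2 and grade 3 events. Its rintatolimod action is "Hold therapy until resolved to Grade 1 or baseline; reduce future doses by 50" (a percentage). The IFN action has the same form with a 75% cut.
- Section 10.2.1 covers non-hematologic toxicity and is introduced by "For grade 3 toxicity not addressed in Table 2". For rintatolimod it reads "1st episode: dose will be held and restarted at the next study visit at a dose reduction by 50%. The dose can be re-escalated", on condition that the toxicity has fallen to grade 1 or less, or to baseline. The IFN text is the same with 75%.

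**Number of doses.** Section 10.4 plans two doses. Section 10 lets Expansion Cohort patients receive further rintatolimod infusions at the PI's judgment, up to 12. That cohort receives no IFN (Section 19.1). Section 32.2.2 describes the bottle as "containing 200 mg (100 mg in case of toxicity) per 80 mL", which matches a 50% reduction.

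**The concern.** These are instructions that a treating team would follow after a grade 3 event, so each should lead to one dose.

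In the pancreatitis row, the percentage and the bracketed figure agree at one dose level out of three. A patient at 5 MU/M2 dosed by the bracket would receive an unchanged dose after an event that, if at least possibly related and within Days 1 to 7, meets the DLT definition in Section 10.2.2.

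In Section 10.2.1, recovery to grade 1 or baseline plays a different part from the one it plays in Table 2. In the table it is the condition for resuming at the reduced dose. In 10.2.1 the drug resumes at the reduced dose without it, and recovery becomes the condition for going back up. A recovered patient could therefore be given 100 mg under one text and 200 mg under the other, and a patient who has not recovered could be redosed under one text and held under the other.

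**Working it through.** **1. Pancreatitis row.** Inputs: IFN levels 5, 10 and 20 MU/M2 (Table 1); a 75% reduction and a bracketed 5 MU/M2 (Table 2). At level 0 no IFN is given.

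Dose after a 75% cut = 0.25 × dose. Cut implied by the bracket = 1 − 5/dose.

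- From 20: 0.25 × 20 = 5, which reproduces the plan's figure. The implied cut is 1 − 5/20 = 75%.
- From 10: 0.25 × 10 = 2.5. The implied cut is 1 − 5/10 = 50%, and the bracket is 5 − 2.5 = 2.5 MU/M2 too high.
- From 5: 0.25 × 5 = 1.25. The implied cut is 1 − 5/5 = 0%, and the bracket is 5 − 1.25 = 3.75 MU/M2 too high.

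Reach: IFN is given on Day 1 and Day 3 or 4, so at most one dose follows an event. The row holds that dose, and Section 10.2 does not make up a missed one. A reduced IFN dose is given only if the event settles in time for Day 3 or 4.

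Patients treated at the two affected levels: the Phase I maximum of 24 over four levels is 6 per level, so 6 + 6 = 12. If the MTD were 5 or 10, adding the 10 Phase IIa patients gives 12 + 10 = 22. This counts patients exposed to those levels, not patients affected. It also rests on a total of 24 + 10 = 34, while Section 4.1 allows up to 44.

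**2. Overlap of Section 10.2.1 with Table 2.** Read literally, the catch-all row already covers every other clinically significant grade 3 event, so 10.2.1 is left with almost nothing. It has real scope only if its introductory line is taken to mean events without a named row, grade 3 fatigue for example. On that reading both texts apply to the same event, with different restart conditions and different later doses.

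**3. Where re-escalation can act.** It needs at least three infusions: full dose with the event, reduced dose, then re-escalated dose.

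- Main Cohort: 2 doses, fewer than 3, so neither drug can be re-escalated.
- Expansion Cohort: up to 12 rintatolimod infusions, so 200 to 100 to 200 mg is possible. There is no IFN to re-escalate.

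**4. Ceiling for rintatolimod.** The reduced dose is 0.5 × 200 = 100 mg. If the first grade 3 event follows infusion k, infusion k+1 is reduced under either text. Infusions k+2 to 12, which number 11 − k, can then differ by 100 mg each.

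- k = 1: 10 infusions, 1,000 mg (infusions 2 to 12 total 11 × 100 = 1,100 mg against 100 + 10 × 200 = 2,100 mg).
- k = 6: 5 infusions, 500 mg.
- k = 11: 0 infusions.

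These figures assume that all 12 infusions are given and that there is no second episode, since a second episode ends treatment under 10.2.1.

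**The case against.** There are four good arguments on the other side.

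- **The pancreatitis instruction is the percentage.** The bracket looks like an illustration carried over from the 20 to 5 reduction in Section 2.5, and reading it as no cut contradicts the words just before it. This makes a dosing error unlikely, but it does not make the bracket correct at 5 or 10.
- **Section 10.2.1 may have no live scope.** If the catch-all row takes every clinically significant grade 3 event, Table 2 and 10.2 govern and nobody is re-escalated. That limits the reach. It also means the re-escalation sentences serve no purpose and can be removed at no cost.
- **The 10.2 sentence may not have been written for extended Expansion dosing.** It refers to the two-drug combination and a short course. Section 10 says weeks of rintatolimod may be needed for sustained activation, which could favour a return to 200 mg. This stands: whether to allow re-escalation there is partly the sponsor's choice, but the protocol should state the choice once.
- **Clinical judgment intervenes.** Section 10 and the Expansion calendar footnotes leave further infusions to the PI in the light of attributed AEs, and Section 10.2 leaves discontinuation to the physician. That settles whether to infuse again. The only dose named there is the nominal 200 mg, so it does not settle which rule sets the dose after a reduction.

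A reader might infer that Main Cohort patients could be escalated back to full-dose IFN. The two-dose schedule rules that out. Giving Day 3 in full once toxicity settles would contradict the instruction in 10.2.1 to restart at a reduced dose. A reader might also infer a demonstrated hazard from 200 rather than 100 mg. Section 13.2 reports doses up to 1200 mg twice weekly without dose-limiting organ toxicity, so the documents do not support that inference.

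**Conclusion.** Both inconsistencies are real and both are minor. The bracketed 5 MU/M2 is wrong at two of the three active IFN levels, by 2.5 and 3.75 MU/M2. It can affect at most one later dose per patient, and will seldom affect any. Section 10.2.1 departs from Table 2 on the restart condition and from Section 10.2 on re-escalation. Its scope is narrow: grade 3 non-hematologic events that Table 2 is taken not to address. Re-escalation can act only for Expansion Cohort rintatolimod beyond two infusions.

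The 1,000 mg figure and the counts of 12 and 22 patients are remote ceilings. It would be a mistake to read them as expected impact. The first needs a related grade 3 event at the first infusion followed by all 12 infusions without a second episode. The patient counts are of those treated at the two levels, and 22 depends on a total that the protocol does not fix. No endpoint, sample size or analysis changes.

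**What to change.** 1. In the Table 2 pancreatitis row, delete the bracketed dose, or state that it applies only at the 20 MU/M2 level, so that the 75% reduction governs at every level.
2. In Section 10.2.1, make the restart condition the same as in the Table 2 catch-all row for both drugs: hold until grade 1 or baseline, then resume at the reduced dose. Keep the rule that a second episode ends treatment.
3. Delete the two re-escalation sentences from Section 10.2.1 so that it agrees with Section 10.2. If the sponsor wants re-escalation during extended Expansion dosing, say so in Section 10.2 for that cohort only.

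The cost is a few words in Section 10.2.1 and one cell of Table 2, with one sentence in Section 10.2 if re-escalation is kept for the Expansion Cohort. No patients, procedures or analyses are added.
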